5.3 Trial rationale

This phase 2b trial will be the first clinical trial to investigate the cream formulation in subjects with AD.

The purpose of the trial is to establish a dose-response signal and to evaluate the efficacy and safety of delgocitinib (1, 3, 8 and 20 mg/g) formulated as a cream for topical use, in the treatment of subjects with mild to severe AD. The results from this trial will support further development in phase 3 with regards to e.g. dose selection and treatment duration.

There is a clear unmet need for new treatment options in the treatment of patients suffering from AD. Based on the currently available non-clinical and clinical data, delgocitinib has the potential to become a novel local-acting anti-inflammatory and immunosuppressive agent with skin barrier improving properties (Amano et al. 2015) for topical use in AD. There is a reasonable expectation that delgocitinib in a cream formulation will prove to be an effective and well-tolerated treatment based on the mechanism of action, and thereby facilitate the everyday lives of affected patients.

Delgocitinib was originally developed as an ointment and this formulation has been used in all clinical trials performed so far with topical administration. A cream formulation has now been developed for further clinical development with the main purpose of optimising the skin delivery and increase patient-friendliness. Delgocitinib cream contains a relatively low amount of lipid, which facilitates fast absorption into the skin and leaving the skin less greasy following treatment relative to the ointment.

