14.3.4 Testing strategy

This is a dose-ranging trial with the primary objective to establish the dose-response relationship. For the primary endpoint, change from baseline to Week 8 in EASI score, and the secondary endpoints, EASI75 at Week 8 and vIGA-AD TS, the selection of the dose-response model that fits data best will be controlled using a family-wise error rate of 5%. There will be no adjustment for the multiple testing of primary and secondary endpoints, all p-values will be considered nominal.

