14.3.5 Analysis of primary efficacy endpoint

The primary endpoint, change from baseline to Week 8 in EASI, will be analysed for the full analysis set and for the per protocol analysis set. The per protocol analysis is regarded as supportive.

For the analysis of the change from baseline to Week 8 in EASI, data collected after permanent discontinuation of IMP or after initiation of rescue medication will not be included in the analysis. Missing data at Week 8 will be imputed using the MMRM predicted values from the below specified model for repeated measurements.

The MCP-Mod approach (see e.g. [EMA Qualification Opinion of MCP-Mod](#) or [Bretz et al. 2005](#) for further details of the framework) will be used to guide dose selection. The dose-response relationship for the continuous endpoint Change from baseline to Week 8 in EASI will be modelled by the following 3 identified candidate models. These candidate models are selected based on the expected dose-response.

Linear in log: $E_0 + \delta \times \log(d + c)$,

E_{max}: $E_0 + E_{\max} \times d / (ED_{50} + d)$,

Sigmoid E_{max}: $E_0 + E_{\max} \times d^h / (ED_{50}^h + d^h)$,

where d is the dose (incl. vehicle), E_0 is the efficacy offset (anticipated vehicle effect), E_{\max} is the asymptotic maximum effect, ED_{50} is the half-life value of E_{\max} , h is the steepness at ED_{50} , δ is the slope parameter, and c is a fixed offset parameter.

The models will be adjusted for the stratification variables region and disease severity (baseline vIGA-AD of 2, 3, and 4). The model parameters (ED_{50} , h) will be prespecified a priori by suitable guesses based on data from Japan Tobacco's dose-ranging trial QBA2-1 (Nakagawa et al. 2018). Akaike's Information Criteria will be used as the goodness-of-fit criterion that will drive the selection of the dose-response model that fits data best while controlling the family-wise error rate at 5%. Based on the selected model, the dose-response relationship will be estimated and presented with 2-sided 95% CI. If none of the candidate models converge, other possibilities of models and goodness-of-fit criteria will be explored. The dose-response modelling will be performed on both the total population and subjects having a baseline vIGA-AD of 3 or 4, in order to further explore heterogeneity in the disease population.

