In addition to the dose-response modelling approach, the continuous endpoint will be analysed using an MMRM on the post baseline responses up to Week 8 with an unstructured covariance matrix, Kenward-Roger approximation to estimate denominator degrees of freedom, and the mean modelled as follows:

Change from baseline in EASI

$$= \text{treatment} \times \text{visit} + \text{baseline EASI} \times \text{visit} + \text{region} + \text{baseline vIGA-AD}$$

The estimates will be presented with nominal p-values and 95% CI at each visit. The primary comparison between each delgocitinib dose and vehicle will be at Week 8.

Sensitivity analysis will be performed as applicable in order to assess the robustness of results of the primary analysis with respect to the retrieved data at Week 8 and assumptions regarding missing data. This will be described in further detail in the statistical analysis plan.

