14.3.12 General principles

Unless otherwise stated, all significance tests will be 2-sided using the 5% significance level. All CIs will be presented with 95% degree of confidence.

An observed-cases approach will be used for tabulations of data by visit (i.e. involving only those subjects who attended each specific visit).

Categorical data will be summarised using the number and percentage of subjects in each category and treatment group. Continuous data will be summarised using the mean, median, standard deviation, minimum, and maximum values.

All the analyses specified in the protocol will be reviewed in relation to the blinded data actually obtained and the statistical analysis plan will be finalised before breaking the randomisation code.

Any changes from the statistical analysis planned in this clinical trial protocol will be described and justified in a protocol amendment, the statistical analysis plan and/or in the CTR dependent on the type of deviation.

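### The primary MCP-Mod analysis fills each missing Week 8 EASI with one MMRM-predicted value and does not carry the imputation uncertainty into the 5% error rate or the 95% CI

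*Combined protocol and SAP*

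**What the plan says.** Section 14.3.5 applies MCP-Mod to the change in EASI at Week 8. Two rules fix the data that enter it. First, "data collected after permanent discontinuation of IMP or after initiation of rescue medication will not be included in the analysis". Second, "Missing data at Week 8 will be imputed using the MMRM predicted values from the below specified model for repeated measurements". Three candidate shapes are fitted with adjustment for region and baseline vIGA-AD, Akaike's criterion picks one, and "the dose-response relationship will be estimated and presented with 2-sided 95% CI". Section 14.3.4 adds that "the selection of the dose-response model that fits data best will be controlled using a family-wise error rate of 5" per cent.

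In parallel, "the continuous endpoint will be analysed using an MMRM on the post baseline responses up to Week 8 with an unstructured covariance matrix". That model uses Kenward-Roger degrees of freedom and includes baseline EASI by visit as well as region and vIGA-AD.

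Section 14.3.13 only points back to the individual analysis sections. Sensitivity analyses are promised on retrieved Week 8 data and on missing-data assumptions, with the methods left to the SAP. Nothing in the text gives a random draw, a number of imputations, a pooling rule, or a transfer of the MMRM covariance into MCP-Mod. It is also not stated whether the predicted value is subject-specific or the model mean.

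**The concern.** On its plain reading the rule puts one deterministic number in place of each missing score. That number lies on the fitted model and carries no residual scatter, yet it counts as a full observation. Residual variance is then understated and degrees of freedom are overstated, so the MCP-Mod standard errors are too small.

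The design produces such values. Rescue ends IMP treatment (sections 9.5 and 10.2.1). Subjects who stop early are asked back at Week 8 (section 10.3), but that value is excluded from this analysis. Nobody is replaced (section 10.1). Every early stopper or rescued subject therefore becomes a filled-in Week 8 score.

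At stake are the error rate and interval claimed for the curve that is to guide dose choice: "The results from this trial will support further development in phase 3 with regards to e.g. dose selection and treatment duration". The likely practical harm is a dose-response curve that looks more precise than it is.

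**Working it through.** **1. The plan's own figure.** Section 14.1 gives a difference of 7, SD 9, 50 per group and a 5% level (two-sided by section 14.3.12). SE = 9 × √(2/50) = 1.80, and power = Φ(7/1.80 − 1.96) = Φ(1.93) = 97.3% (97.1% with the noncentral t). With 35 and 40 per group, power is 90.2% and 93.5%. The stated figures of at least 95% and about 90% reproduce. The SE of 1.80 is the complete-data benchmark below.

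**2. Why the SE shrinks.** Let a share m be missing at random and filled with the model mean. The filled values add almost nothing to the residual sum of squares, so the residual variance is about σ²(1 − m). The analysis divides this by n, giving an apparent variance of an arm mean of σ²(1 − m)/n. The true variance is about σ²/[n(1 − m)]. The ratio of apparent SE to true SD is therefore about 1 − m, or 0.80 at m = 20%. Simulation gave 1.608/2.002 = 0.80 for 20 mg/g versus vehicle (visit correlation 0.5). Subject-specific prediction recovers part of the loss: 1.663/1.970 = 0.84 in the same setting.

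**3. Simulated family-wise error.** The documents give no missing rate, visit correlation, ED50, h or c, so all are assumed. Two separately coded simulations used 5 arms of 50, five post-baseline visits, SD 9 and monotone dropout, and analysed the filled data as if observed.

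- *A:* the plan's MMRM fitted by REML. Baseline EASI explains 0% or 40% of Week 8 variance; residual adjacent-visit correlation is 0.6 or 0.9; severity mix 30/50/20%; region 80/20%. ANCOVA has 242 df. The test is two-sided max-|t| over three contrasts (log-linear c = 1; Emax ED50 = 2; sigmoid ED50 = 4, h = 3) with critical value 2.140. There were 2,500 trials per cell (Monte Carlo SE 0.4–0.8 points).
- *B:* visit correlation 0.5 or 0.7, one continuous covariate, and a one-sided 5% contrast test with critical value 1.823 (offset 0.2; ED50 = 3; sigmoid ED50 = 5, h = 3). There were 6,000 trials per scenario.

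Actual error (%) at nominal 5%:

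| Missing | A, subject-specific | A, model mean | B, subject-specific | B, model mean |
|---|---|---|---|---|
| 5% | 4.9–5.9 | 5.4–6.3 | 5.3–5.6 | 5.7–5.9 |
| 10% | 5.7–7.6 | 6.9–8.5 | 6.3–6.4 | 6.7–7.5 |
| 20% | 6.6–12.2 | 9.7–13.8 | 7.9–8.9 | 10.0–10.3 |
| 30% | 7.8–16.7 | 11.3–19.2 | 9.4–11.0 | 12.7–13.7 |

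Complete data gave 4.4–5.7% (A) and 4.6–5.2% (B), so the excess comes from the filling step. Outcome-dependent dropout under missing at random (B, 20% missing, correlation 0.6) gave 8.2% and 9.8% for the two readings. In A, apparent SE over true SD for the log-linear contrast (subject-specific) was 0.90–0.97, 0.81–0.94 and 0.73–0.91 at 10%, 20% and 30% missing.

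**4. Coverage of the 95% CI.** In A the 20 mg/g effect versus vehicle was read from the AIC-selected curve (true Emax curve, ED50 = 2, difference 7; delta-method CI; 2,000 trials per cell). Complete data gave 94–96%; filled data gave 92–95%, 88–94% and 86–93% at 10%, 20% and 30% missing. Bias was at most 0.2 EASI points. In B the pairwise difference (subject-specific) was covered 93.1–93.3%, 90.3–91.6% and 87.0–89.2% of the time.

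**5. Does carrying the uncertainty forward repair it?** Generalised MCP-Mod on the MMRM estimates gave error of 4.4–6.0% in all 16 cells of A and curve coverage of 94–96%. Multiple imputation (20 imputations) gave 3.6–6.4% in A at 20–30% missing. In B (correlation 0.6) it gave 5.9%, 6.0% and 4.9%, with coverage 94.7%, 94.7% and 95.7%, at 10%, 20% and 30% missing.

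**The case against.** The protocol does not say outright that the completed data are treated as observed, and "the statistical analysis plan will be finalised before breaking the randomisation code", so the variance step could still appear there. The missing rate is unknown: at 5% missing the effect is close to nothing, and the largest figures need 20–30% missing together with weak prediction or the model-mean reading. A baseline EASI that explains none of the Week 8 change is a pessimistic corner. All p-values are called nominal, this is a phase 2b trial, the curve's location is sound, and the parallel MMRM gives valid dose-versus-vehicle intervals.

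Most of this stands as a limit on size. It does not repair the primary analysis. Section 14.3.5 states a filling rule and section 14.3.13 makes it the operative one, so following the text as written leaves out the variance. The nominal label concerns multiplicity across endpoints; 5% control within each endpoint is still claimed, and the curve's CI is a separate claim. A sensitivity analysis by multiple imputation may be planned, since its methods are not given, but it would sit beside the primary result and not correct it.

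**Conclusion.** The concern holds and should be fixed. If the filled data are analysed as observed, the claimed 5% family-wise error rate and 95% CI are not assured. The effect is slight at 5% missing and material from about 10–20%. The model-mean reading is worse at every missing rate. The lower ends of the ranges apply when baseline and earlier visits predict Week 8 strongly, and with still stronger prediction they could approach 5%.

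The direction follows from the rule itself. The size rests on the assumed missing rate, dropout timing, correlations and candidate-model guesses. Point estimates remain about unbiased under missing at random, so the main consequence is overstated precision of the dose-response curve.

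**What to change.** In section 14.3.5 and the SAP, before unblinding, remove the single imputation. Take the Week 8 dose-group estimates and their covariance matrix from the MMRM already specified, and use them in generalised MCP-Mod for the contrast tests, model fits, information criterion and curve CI. Alternatively, impute multiply under the same missing-at-random model, obtain the MCP-Mod estimates in each completed data set and pool them by Rubin's rules. If single prediction is kept for any purpose, state which prediction is meant and how its uncertainty enters the tests and the CI. The estimand and the missing-at-random assumption do not change.

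The cost is SAP wording and a little programming in the software already named; no new data or subjects are needed. The first option adjusts for baseline EASI as well as region and vIGA-AD, and uses a normal approximation. Intervals widen to their proper length. From the SE ratios in A, for the same estimator, that is 3–11% at 10% missing (1/0.97 to 1/0.90), 6–23% at 20% (1/0.94 to 1/0.81) and 10–37% at 30% (1/0.91 to 1/0.73).

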8.2 Inclusion criteria

For inclusion into this trial, subjects must fulfil all of the following criteria:

1. Signed and dated informed consent has been obtained prior to any protocol-related procedures.
2. Age 18 years and above.
3. Diagnosis of AD as defined by the Hanifin and Rajka criteria for AD ([Hanifin & Rajka 1980, Appendix 6](#)).
4. History of AD for ≥ 1 year.
5. AD involvement of 5–50% treatable body surface area at screening and at baseline (excluding scalp).
6. Disease severity graded as mild to severe according to vIGA-AD (i.e. vIGA-AD ≥ 2) at screening and baseline.
7. Able and willing to follow trial procedures including application of IMP to all AD lesions.
8. A woman of childbearing potential* must use a highly effective** form of birth control throughout the trial and at least for 2 weeks after last application of IMP.
* A woman is defined as not being of childbearing potential if she is postmenopausal (at least 12 months with no menses without an alternative medical cause prior to

screening), or surgically sterile (hysterectomy, bilateral salpingectomy, or bilateral oophorectomy).

**A highly effective method of birth control is defined as one which results in a low failure rate (less than 1% per year) such as bilateral tubal occlusion, intrauterine device, intrauterine hormone-releasing system, combined (oestrogen and progestogen containing) hormonal contraception associated with inhibition of ovulation (oral, intravaginal, transdermal), progestogen-only hormonal contraception associated with inhibition of ovulation (oral, injectable, implantable), sexual abstinence (when this is in line with the preferred and usual life style of the subject), vasectomised partner (given that the subject is monogamous).

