11.3 Efficacy assessments

11.3.1 Eczema Area and Severity Index (EASI)

The EASI is a validated measure used in clinical practice and clinical trials to assess the severity and extent of AD ([Hanifin et al. 2001](#), [Tofte et al. 1998](#)). The EASI score will be assessed according to the schedule of trial procedures (Section 4). The assessment will be based on the condition of the disease at the time of evaluation and not in relation to the condition at a previous visit.

The EASI is a composite index with scores ranging from 0 to 72, with higher values indicating more severe or more extensive condition. The index will be calculated as shown in [Panel 8](#). Briefly, the investigator will assess the severity of 4 AD disease characteristics (erythema, induration/papulation, excoriation, and lichenification) on the 4 body regions (head/neck, trunk, upper extremities, lower extremities); severity will be assessed according

to the scale shown in Panel 9. For each body region, a severity sum score will be calculated which will be multiplied by an area score (Panel 9) and by a weighting factor. The EASI score equals the sum of the scores obtained for each body region (Panel 8). The EASI score will be calculated automatically.

Panel 8: Calculation of the Eczema Area and Severity Index

Body region	Erythema	Induration/ papulation	Excoriation	Lichenification	Area score	Weighting factor	Score
Head/neck	(SS +	SS +	SS +	SS)	x AS	x 0.1	
Trunk	(SS +	SS +	SS +	SS)	x AS	x 0.3	
Upper extremities	(SS +	SS +	SS +	SS)	x AS	x 0.2	
Lower extremities	(SS +	SS +	SS +	SS)	x AS	x 0.4	
The EASI score is the sum of the 4 body region scores							  (range 0–72)

AS, area score; EASI, Eczema Area and Severity Index; SS, severity score. Modified from (HOME website).

Panel 9: EASI severity score scale and area score scale

Severity score scale	
0	None/absent
1	Mild
2	Moderate
3	Severe

Note: half-steps (0.5, 1.5, 2.5) are allowed.

Area score scale	
0	0% affected area
1	1% to 9% affected area
2	10% to 29% affected area
3	30% to 49% affected area
4	50% to 69% affected area
5	70% to 89% affected area
6	90% to 100% affected area

EASI, Eczema Area and Severity Index

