11.3.2 Validated Investigator Global Assessment scale for Atopic Dermatitis (vIGA-AD)

The vIGA-AD is an instrument used in clinical trials to assess the subject's global disease severity and is based on a 5-point scale ranging from 0 (clear) to 4 (severe) (Panel 10). The vIGA-AD score will be assessed at time points according to the schedule of trial procedures (Section 4). The assessment will be based on the condition of the disease at the time of evaluation and not in relation to the condition at a previous visit. New lesions that occurred on previously untreated areas will be included in the assessment.

The vIGA-AD score is selected using the descriptors in Panel 10 that best describe the overall appearance of the lesions at a given time point. It is not necessary that all characteristics under morphological description be present.

Panel 10: Validated Investigator Global Assessment scale for Atopic Dermatitis

Score	Morphological description
0 - Clear	No inflammatory signs of atopic dermatitis (no erythema, no induration/papulation, no lichenification, no oozing/crusting). Post-inflammatory hyperpigmentation and/or hypopigmentation may be present.
1 - Almost clear	Barely perceptible erythema, and barely perceptible induration/papulation, and/or minimal lichenification. No oozing or crusting.
2 - Mild	Slight but definite erythema (pink), slight but definite induration/papulation, and/or slight but definite lichenification. No oozing or crusting.
3 - Moderate	Clearly perceptible erythema (dull red), clearly perceptible induration/papulation, and/or clearly perceptible lichenification. Oozing and crusting may be present.
4 - Severe	Marked erythema (deep or bright red), marked induration/papulation, and/or marked lichenification. Disease is widespread in extent. Oozing or crusting may be present.

Reference: [Eli Lilly and Company 2017](#)

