14.1 Sample size

A total of 250 subjects will be randomised 1:1:1:1:1 to one for the following 5 treatment groups: delgocitinib cream 1 mg/g, 3 mg/g, 8 mg/g, 20 mg/g or delgocitinib cream vehicle.

The sample size is based on the following pairwise consideration, even though the primary objective of the trial is to establish the dose-response relationship: With a significance level of 5% when comparing two treatment groups and assuming a difference in the mean change from baseline to Week 8 in EASI of 7 (with a standard deviation of 9 for each treatment group) between an investigational dose (delgocitinib cream) and delgocitinib vehicle, then 50 subjects per treatment group will provide a nominal power of at least 95% to detect a difference between two treatment groups. With 35–40 subjects per treatment group (e.g. in the subgroups of subjects with moderate or severe AD), there is approximately 90% power to detect a difference of 7 in mean change from baseline to Week 8 in EASI.

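### The primary dose-response models leave out baseline EASI, which the MMRM in the same section includes, and so give up precision at almost no saving

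*Combined protocol and SAP*

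**What the plan says.** Section 14.3.5 fits three candidate dose-response models (linear in log dose, Emax, sigmoid Emax) to the change in EASI from baseline to Week 8. On covariates it says: "The models will be adjusted for the stratification variables region and disease severity (baseline vIGA-AD of 2, 3, and 4". No other covariate is named. The modelling is done for the total population and again for subjects with baseline vIGA-AD 3 or 4.

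The same section adds an MMRM for the same endpoint. Its mean model has treatment by visit, baseline EASI by visit, region and baseline vIGA-AD. That MMRM also feeds the primary analysis: "Missing data at Week 8 will be imputed using the MMRM predicted values from the below specified model for repeated measurements".

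Section 14.1 sizes the trial on a pairwise difference of 7 EASI points with a "standard deviation of 9 for each treatment group" and 50 subjects per arm, and states a nominal power of at least 95%. With 35–40 per arm it states about 90%.

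**The concern.** The endpoint is an absolute change, so a subject cannot improve by more than the baseline score. Some relation between baseline EASI and change is therefore to be expected, and vIGA-AD class captures it only coarsely. EASI multiplies sign severity by an area score. The vIGA-AD grades describe morphology, and only grade 4 mentions extent ("Disease is widespread in extent"). Eligibility admits "AD involvement of 5–50% treatable body surface area", so extent can differ widely within one class.

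Variation in baseline EASI within a class then stays in the error term of the dose-response models, and the confidence band around the fitted curve is wider than necessary wherever baseline predicts change. This matters most where the sample size section offers no assurance: effects of lower doses, differences between neighbouring doses, and the smaller vIGA-AD 3–4 analysis. The MMRM does give baseline-adjusted pairwise contrasts, but the curve that guides dose selection is not baseline-adjusted.

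**Working it through.** **Inputs from the protocol.** Two-sided 5% level (sections 14.1 and 14.3.12), difference 7, SD 9, 50 per arm, 5 arms, 250 subjects; 35–40 per arm for the subgroup case.

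**Assumed.** The partial correlation r of baseline EASI with change, given region and vIGA-AD class, is not in the documents; 0 to 0.6 is shown. Section 14.1 does not say whether SD 9 is before or after adjustment; it is taken here as the residual SD after the strata.

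**1. The plan's own power.** Two-sample noncentral t with difference 7 and SD 9: 97.1% at 50 per arm, 89.4% at 35, 93.0% at 40. The normal approximation gives 97.3%, 90.2% and 93.6%. The stated figures reproduce; the sample size is not in error.

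**2. Spread of baseline EASI within a class.** Section 11.3.1 gives EASI as the sum over regions of (sum of four sign scores) × area score × weight, with weights 0.1 + 0.3 + 0.2 + 0.4 = 1.0. With every sign at 2 in every region:

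- area score 1: 4 × 2 × 1 × 1.0 = 8
- area score 2: 4 × 2 × 2 × 1.0 = 16
- area score 3 ("30% to 49% affected area"): 4 × 2 × 3 × 1.0 = 24

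Both ends can fall within the eligible body surface area. The same sign severity can thus go with a three-fold range in the largest possible improvement.

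**3. Precision.** Residual degrees of freedom are 250 − (5 arms + 1 region + 2 vIGA-AD) = 242, or 241 with baseline EASI. The half-width of a 95% CI for a dose-vehicle difference is

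t(0.975, df) × 9 × √(1 − r²) × √(2/50),

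times √(1 + 1/240) when the slope is estimated. At r = 0 this is 1.970 × 9 × 0.2 = 3.55. Power is from the noncentral t with the same standard error.

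| r | Variance removed | Half-width | Power at 7 | Power at 4 (assumed) |
|---|---|---|---|---|
| not adjusted | – | 3.55 | 97.2% | 60% |
| 0.2 | 4% | 3.48 | 97.6% | 62% |
| 0.3 | 9% | 3.39 | 98.2% | 64% |
| 0.5 | 25% | 3.08 | 99.4% | 72% |
| 0.6 | 36% | 2.84 | 99.8% | 79% |

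In equivalent sample size, 50/(1 − r²) is about 52, 55, 67 and 78 per arm.

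**4. vIGA-AD 3–4 analysis.** The same formula with 40 and 35 per arm gives 3.97–4.25 unadjusted, 3.90–4.17 at r = 0.2 and 3.45–3.69 at r = 0.5.

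**5. Break-even.** The covariate pays for itself when r² exceeds 1/241, that is r > 0.064.

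**6. Dose-response test rather than a pairwise contrast.** The protocol's guesses for ED50 and h are not given, so shapes were assumed: log(d + 1), Emax with ED50 3, sigmoid Emax with ED50 4 and h 2. The true curve was taken as that Emax, and the two-sided multiplicity-adjusted critical value is 2.08. For a true effect of 5 at the top dose, power is 88% without baseline EASI, 91% at r = 0.3 and 95% at r = 0.5. For an effect of 4 it is 71%, 75% and 83%.

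**7. Common slope.** In 1,500 simulated trials with improvement proportional to baseline (assumed 30% on vehicle to 65% on the top dose), the mean top-dose-versus-vehicle contrast was −4.66 to −4.69 without baseline EASI and −4.67 to −4.70 with it. One common slope did not shift the average contrast. This check was not used to size the gain.

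**The case against.** The strongest reply is that nothing fails. Randomisation protects the dose comparison, adjusting for the stratification factors is a valid analysis, and power at the planned difference is already 97%. The size of the gain rests wholly on an r that the documents do not give: at 0.2–0.3 the half-width moves by only 0.07–0.16 points. All of this stands, and it is why the point concerns efficiency, not validity.

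Some further arguments stand in part:

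- *The half-widths describe a pairwise contrast, which the MMRM already adjusts.* True, but the factor √(1 − r²) acts on the residual error of the fitted curve too, and step 6 shows the effect on the MCP-Mod test under assumed shapes.
- *SD 9 may be the SD before adjustment for strata.* Then the unadjusted half-width is below 3.55 and power at 4 is above 60%. The proportional gain for a given r is unchanged.
- *An imputation model may use predictors that the analysis model omits.* Agreed. The mismatch is not an error in itself. It shows that the plan treats baseline EASI as predictive of this endpoint, yet does not use it in the primary model.
- *The 8-to-24 example shows spread, not prediction.* Correct; it makes r > 0 plausible and does not measure it.
- *Section 14.3.6 carries the modelling approach over to the binary endpoints, where a new covariate changes the conditional effect.* The change proposed here is confined to the continuous primary endpoint.
- *The SAP may settle it.* Section 14.3.12 says that the SAP is finalised before the code is broken. Section 14.3.5 defers only the detail of sensitivity analyses to it, and nothing in the documents promises this covariate for the dose-response models.

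**Conclusion.** The concern holds. The primary MCP-Mod models omit a baseline covariate that the plan already uses for the same endpoint in the same section, without a stated reason. The estimated curve is not biased by this, type I error is not inflated, and the stated power is unaffected.

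The loss is the share r² of residual variance: nil at r = 0, 4–9% at 0.2–0.3, and 25–36% at 0.5–0.6. At the planned difference of 7 it barely matters. It becomes material for effects nearer 4 points, for separating doses and in the vIGA-AD 3–4 analysis, if r is moderate. The figures in EASI points assume SD 9 as the residual SD after strata. The change should be made because it costs almost nothing and serves the analysis on which the dose will be chosen.

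**What to change.** Before unblinding, add baseline EASI as a continuous covariate to the MCP-Mod models for the change in EASI, alongside region and baseline vIGA-AD, in both the total population and the vIGA-AD 3–4 analysis. State that the covariate applies to the continuous primary endpoint and not automatically to the binary ones. State also that a common baseline slope is an approximation if improvement is proportional to baseline.

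An alternative, though not an equivalent, is generalised MCP-Mod on the Week 8 dose estimates from the MMRM and their covariance matrix. This brings in the baseline adjustment and also replaces the stated imputation by predicted values, so it changes the handling of missing data as well.

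The cost of the first option is a sentence in the protocol or SAP and one degree of freedom. Baseline EASI is already scheduled for every subject on Day 1.
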